4.12.4. Electrocardiograms

ECG variables that will be analyzed including: QTc and QRS intervals as well as ECG findings.

ECG summaries will take form of tables for raw data and changes from baseline (values collected during Day 1) as well as percentage of abnormal values for ECG findings. In addition, shift tables presenting number of patients that either developed abnormalities since baseline will be provided.

The number of patients with at least one clinically relevant finding detected during the ECG examination will be summarized in frequency tables for each scheduled assessment or visit.

Change from baseline values of ECG parameters will take form of boxplots for each study arms.

4.12.5. Physical examination

Abnormal findings occurring after screening and baseline visit (after Day 1) will be listed. No summaries are planned.

4.12.6. Chest imaging

Method of imaging as well as date of procedure and result will be listed only. No summaries are planned.

4.12.7. Urinary test for substance abuse, alcohol breath test and pregnancy test

Data regarding urinary test for substance abuse as well as results from pregnancy test will be presented only in listing. No summaries are planned.

A separate listings will be produced for positive results of drug tests and alcohol breath test more than 0.0 (for purpose of presentation in the statistical report/CSR).

4.12.8. Contraception

Listing containing data regarding contraception used will be prepared for each patient. No summaries are planned.

4.12.9. COVID-19 and tuberculosis

Listing containing information about COVID-19 test 72h prior to Day 1 and results of QuantiFERON-TB GOLD (QFT-G) test will be prepared. No summaries are planned.

Separate listing will contain information from COVID-19 questionnaire.

4.12.10. Patient diary

Information whether subject was trained on how to take medication properly, as well as information on patient diary (dispensing, returning, completing consistently with instruction) will be listed only. No summaries are planned.

4.12.11. Contact checklist

Data from contact checklist collected during the phone call visits will be listed only. No summaries are planned.

4.13. Pharmacokinetic analyses

Analyses will be performed for PS and PSPC populations. Concentration data and calculated PK parameters will be listed for PS population, while data summaries, plots, and inference analyses will be performed in PSPC population. In case PS and PSPC (PS = PSPC) are identical, all analyzes will be performed only in PS analysis set.

[figure not shown]
The following pharmacokinetic parameters will be estimated if data permits: $AUC_{(0-6h)}$, C_{max} , T_{max} , K_{el} and $T_{1/2}$ for CPL409116 and its M3 metabolite, individually for each subject and separately for Days 1, 8, 57, and 85. They will be computed using non-compartmental modelling approach using actual sampling times.

All individual pharmacokinetic parameters described above will be presented in listings and analyzed with descriptive summary statistics including arithmetic mean, geometric mean, median, quantiles Q1 and Q3, standard deviation (SD), coefficient of variation (CV), minimum and maximum. Analyses will be performed in subgroups by dose treatment arm.

Plasma concentration/time curves will be presented for CPL409116 and M3 in linear and log-linear scale. Curves will be presented separately for Days 1, 8, 57 and 85 for:

- individual subjects (including additional log-linear scale plot showing points used for K_{el} calculation) (PS population),
- arithmetic mean \pm SD within dose cohort, by dose cohort, in linear scale (PSPC population),
- arithmetic mean within dose cohort, by dose cohort, in log-linear scale (PSPC population),

- overlapping individual curves (with mean curve in different color) for each dose cohort, in linear and log-linear scale (PSPC population).

4.15. Exploratory analyses of pharmacokinetic data

An exploratory PK analysis, not described in the clinical study protocol, will be performed if data permits for both CPL409116 and M3 individually for each subject (and separately for Days 1, 8, 57, and 85, if applicable):

- $AUC_{(0-t)}$ and $AUC_{(0-\infty)}$ on Day 85
- %extrapolated AUC on Day 85
- metabolite-to-parent ratio of C_{max} and $AUC_{(0-6h)}$ – based on molar concentrations
- accumulation calculated as $AUC_{(0-6h)}$ ratios Day 8/Day 1, Day 57/Day 1 and Day 85/Day 1
- accumulation calculated as for C_{max} ratios Day 8/Day 1, Day 57/Day 1 and Day 85/Day 1
- linearity of dose-normalized C_{max} and $AUC_{(0-6h)}$
- evaluation of changes in T_{max} (median and range, individual differences) between doses and days of study
- evaluation of changes in $T_{1/2}$ (mean \pm SD) on Day 85 between doses
- evaluation of changes in CL/F (mean \pm SD) on Day 85 between doses
- evaluation of changes in Vz/F (mean \pm SD) on Day 85 between doses
- $C_{max,ss}$ on Days 8, 57 and 85
- $C_{min,ss}$ on Days 8, 29, 57 and 85
- evaluation of steady-state basing on C_{trough} on Days 8, 29, 57 and 85
- evaluation of intra-subject variability in PK between days 8, 57 and 85
- fluctuation on Day 85
- swing on Days 8, 57 and 85.

Additionally to the PK analyses planned in the study protocol, individual ratios of C_{max} , $AUC_{(0-6h)}$, and $AUC_{(0-\infty)}$ and differences of T_{max} , between CPL409116 and its metabolite M3 will be calculated and listed. Results of assessment of pharmacokinetics will be compared between CPL409116 and its metabolite M3, i.e. descriptive statistics for individual ratios of C_{max} , $AUC_{(0-6h)}$, and $AUC_{(0-\infty)}$ and differences of T_{max} , between CPL409116 and its metabolite M3 will be reported, by dose cohort. To compare results between cohorts, point estimates with 90% confidence intervals for the geometric means ratios between each dose and the middle dose will be calculated based on the ANOVA model for individual CPL409116 and its metabolite M3 ratios for each of the above PK parameters (except differences in T_{max}) with fixed effects for dose, separately for Days 1, 8, 57, and 85 of the study. Dose effect on ratio of CPL409116 and its metabolite M3 PK parameters values will be considered neglectable if the calculated 90% confidence interval for the geometric means ratio will completely within the range of 80.00-125.00%. However, due to the small planned sample size, power of the above analysis will be small and results should be interpreted with caution. Differences in T_{max} will be compared between dose cohorts based on the pairwise comparisons using Mann-Whitney test with Bonferroni correction for multiple comparisons.

Assessment of time to steady-state will be performed using descriptive methods and examination of the descriptive statistics and plots of pre-dose and 2.5 hour post-dose concentrations on Days 1-85. No formal statistical methods of estimation of time to steady-state will be applied. Box-plots for plasma concentration of CPL409116 and its metabolite M3 vs. Day (for Days 1, 8, 29, 57 and 85) will be presented for pre-dose (and 12 h sample for Day 85) and 2.5 h after administration concentrations.

To assess proportionality/linearity of relationship between CPL409116 dose and PK parameters following methods will be applied:

- Plots of mean (\pm SD) PK parameter value versus CPL409116 dose + scatterplot of calculated PK parameters values versus CPL409116 dose, by day of the study, for all calculated PK parameters will be presented.
- Dose-normalized values of C_{max} , $AUC_{(0-\infty)}$, and $AUC_{(0-6h)}$ will be calculated (i.e. PK parameter value will be divided by the corresponding dose) and summarized using descriptive methods by dose treatment arm and study day 1, 8, 57, and 85.
- The log-transformed dose-normalized parameters C_{max} , $AUC_{(0-\infty)}$, and $AUC_{(0-6h)}$ and log-transformed parameters $T_{1/2}$, CL/F , and V_z/F will be analyzed using ANOVA with fixed effects for CPL409116 dose, subject and (if applicable) day 1, 8, 57, and 85 of the study. The least square means will be calculated together with 95% CIs. Estimates of the pairwise geometric means ratios between each dose and the middle dose will be calculated together with 90% confidence intervals. CPL409116 dose effect on CPL409116 PK parameters values will be considered neglectable if the calculated 90% confidence interval for the geometric means ratio will be completely within the range of 80.00-125.00%. However, due to the small planned sample size, power of the above analysis will be small and results should be interpreted with caution.
- PK parameter t_{max} will be compared between doses based on the pairwise comparisons using Mann-Whitney test with Bonferroni correction for multiple comparisons, separately for each of days 1, 8, 57, and 85 of the study.
- Assessment of fit of linear model for log-transformed PK parameter (C_{max} , $AUC_{(0-\infty)}$, and $AUC_{(0-6h)}$) value versus log-transformed CPL409116 dose, separately for day 1, 8, 57, and 85 of the study - the mean slope of the log-transformed parameters against log-dose will be estimated and the corresponding 90% CIs will be constructed; dose-proportionality will be concluded if the slope will not be different from unity.

Additionally intra-subject variability for C_{max} , $AUC_{(0-\infty)}$, and $AUC_{(0-6h)}$ will be estimated based on the results of analysis of variance model with fixed effects for CPL409116 dose, subject and days 8, 57, and 85 of the study.

Exploratory PK analysis results will be presented in the separate part of pharmacokinetic report. The latter one will be an attachment to the Clinical Study Report. Additional PK parameters, not listed above, may be determined where appropriate.

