2.2. Study design

This is a 12-week, phase II, multicentre, randomised, double blind, efficacy and safety study of CPL409116 in participants with active rheumatoid arthritis who are taking methotrexate but have an inadequate response to this drug.

Approximately 100 male and female subjects are to be enrolled in the study. Eligible subjects are to be randomized into one of the 4 treatment arms determined in points below:

- 25 are to be randomized to the treatment arm with CPL409116 at a dose of 60 mg BID;
- 25 are to be randomized to the treatment arm with CPL409116 at a dose of 120 mg BID;
- 25 to the treatment arm with CPL409116 at a dose of 240 mg BID;
- 25 to the treatment arm with placebo.

Randomisation ratio is to be: 1:1:1:1. This will be the age-stratified randomisation. In all treatment arms investigated product/ placebo is to be administered orally for 12 weeks in a blinded fashion. In order to maintain the blind and minimize bias, all subjects will receive the same number and types of tablets each day of treatment.

The study consists of 3 phases:

- A Screening phase of up to 4 weeks,
- A double-blind treatment phase (Day 1 to Day 85/86; 12 weeks) with two doses of IMP administration per day (except Day 85 when patients are to ingest only one dose of IMP in the morning and except Day 86 without administration of CPL409116, when the last sample of blood will be collected for PK analysis in the morning),
- A 4 weeks post-treatment follow-up phase up to Week 16 (Day 113). Patients are to come to a study centre two times after the last dose of IMP. According to the schedule assessment in the follow-up period are planned two ambulatory visits and phone calls from clinical centres: Week 14 and 16 (Day 99 and 113 respectively)- an ambulatory visit; Week 13 and 15 (Day 92 and 106 respectively)- phone call from a clinical centre. The end of the study is planned at Week 16 (Day 113).

[figure not shown]

Figure 1. Study design

In the **Screening Period**, patients undergo screening assessments from Day -28 to Day 0. Rolling admission is employed in this study. Patients that fulfil all the inclusion criteria and none of the exclusion criteria will be considered eligible for this study. Subjects must complete all screening procedures and assessments and have test results available prior to the Baseline visit (Visit 2).

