2.3. Sample size

Sample size calculation for a trial with a continuous outcome measure defined as change from baseline was determined based on simulation of analysis of covariance (ANCOVA) where the baseline measure, treatment and clinical site are included as covariates in the analysis. The value assumptions were adopted from a published data. The outcome measure DAS28-CRP, measured at baseline and at 12-week postintervention. A decrease in the DAS28-CRP score indicates an improvement in health status. Assuming the baseline mean scores are the same for drug and placebo arms and equal to 5.5 (with standard deviation equal to 1.0). We assume 12-week mean score for drug equal to 3.7 (SD = 1.1) and for placebo 4.5 (SD = 1.1). With 21 patients per group, the study has >80% power to detect a difference of 0.8 points or greater compared to placebo, given 5% significance level. Assuming a 16% dropout rate the study will enroll approximately 100 subjects.

3. General aspects of the statistical analysis

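### The 80.00-125.00% rule for a negligible dose effect never tests 240 mg against 60 mg; false negligible calls over that span can exceed 5%, but only if between-subject CV is low (minor)

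*SAP*

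**What the plan says.** SAP 4.15 uses the same rule in two places.

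- **CPL409116/M3 ratios** (Cmax, AUC(0-6h), AUC(0-inf)): an ANOVA "with fixed effects for dose, separately for Days 1, 8, 57, and 85 of the study" gives the estimates, and "point estimates with 90% confidence intervals for the geometric means ratios between each dose and the middle dose will be calculated". The decision is: "Dose effect on ratio of CPL409116 and its metabolite M3 PK parameters values will be considered neglectable if the calculated 90% confidence interval" meets the limits, that is, the "confidence interval for the geometric means ratio will completely within the range of 80.00-125.00" per cent.
- **Dose-normalised Cmax and AUCs, and T1/2, CL/F and Vz/F**: "Estimates of the pairwise geometric means ratios between each dose and the middle dose will be calculated together with 90% confidence intervals", with the same limits and the same conclusion. The model here has fixed effects for dose, subject and, where applicable, day.

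In both places the SAP adds that "due to the small planned sample size, power of the above analysis will be small and results should be interpreted with caution". It labels the whole analysis exploratory and absent from the protocol. For Cmax and the AUCs only, it also fits log parameter on log dose by day, with a 90% interval for the slope, and concludes dose-proportionality if the slope does not differ from 1. It gives no between-subject CV, error rate or numerical power for the rule.

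**The concern.** The conclusion is worded as being about the dose effect, and the doses run from 60 to 240 mg. The evidence consists of two adjacent contrasts that share 120 mg as reference. If exposure or the metabolite ratio drifts steadily with dose, the largest difference lies between 60 and 240 mg, and the rule does not form that contrast. Tmax, in the same section, is compared pairwise between doses with no middle-dose restriction.

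A 90% interval inside fixed limits is two one-sided tests at 5%, so each contrast carries a 5% risk of a false negligible call at its own limit. That protection does not extend to a pair of doses that is not tested. A pharmacokinetic report attached to the Clinical Study Report could then describe dose-independent kinetics, or a dose-independent metabolite ratio, when the lowest and highest doses differ by the SAP's own limit or more.

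**Working it through.** **No figure in the plan to reproduce.** The documents state no power or error rate for this rule.

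**Inputs**
- Limits 0.80 and 1.25 (SAP 4.15), or ±ln 1.25 = ±0.2231 on the log scale.
- 25 per active arm (SAP 2.2); after 16% dropout (SAP 2.3), 25 × 0.84 = 21.
- One-way ANOVA by day, as for the CPL409116/M3 ratios, with 3(n − 1) error df: 72 for n = 25 and 60 for n = 21.
- Assumption: log-normal data, CV varied because it is not given. Log-scale SD is σ = √ln(1 + CV²).

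**Bound.** If both true steps are inside 1.25, the 240:60 ratio can reach 1.25 × 1.25 = 1.5625.

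**Why low CV matters.** Put a true 240:60 ratio of 1.25 into two equal steps of √1.25 = 1.118, log 0.1116. The 90% half-width for a contrast is t × σ × √(2/n).
- CV 20%, n = 25: 1.666 × 0.198 × √(2/25) = 0.093. An estimated step passes up to 0.2231 − 0.093 = 0.130 (ratio 1.14). The true step of 0.1116 is below that, so each contrast usually passes.
- CV 30%, n = 25: 1.666 × 0.2936 × √(2/25) = 0.138. An estimated step passes only up to 0.085 (ratio 1.09). The true step is above that, so each contrast usually fails.

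**Joint rate.** The two contrasts are correlated through 120 mg, so the joint probability was simulated (at least 400,000 trials per cell). As a check, with a true 240:120 ratio of 1.25 that single contrast passes 5.0-5.1% of the time, as it should.

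Chance that both planned intervals lie inside 80-125%, true 240:60 = 1.25 in equal steps:

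| CV | n = 21 | n = 25 | n = 25, 240:60 added |
|---|---|---|---|
| 10% | 94.7% | 97.7% | 5.0% |
| 15% | 56.3% | 67.6% | 4.9% |
| 20% | 24.3% | 32.8% | 4.4% |
| 25% | 10.6% | 14.9% | 3.7% |
| 30% | 5.1% | 7.3% | 2.9% |
| 35% | 2.4% | 3.8% | 2.1% |
| 40% | 0.9% | 1.9% | 1.2% |

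The rate crosses 5% at a CV of about 30% (n = 21) or 33% (n = 25).

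**Other true effects, n = 25**
- Ratio 1.30 in equal steps: 16.5% at CV 20%, 6.9% at 25%, 3.3% at 30%.
- Ratio 1.40: 2.0% at CV 20%. Ratio 1.50: at most 0.6% at any CV tried (10-60%).
- Ratio 1.25 lying wholly between 120 and 240 mg: 4.6% at CV 20%, because an existing contrast catches it.

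**Slope analysis.** The log doses are equally spaced by ln 2, so with equal arms the fitted slope changes by (log mean at 240 − log mean at 60)/(2 ln 2). It depends only on the 240-to-60 difference. A dose-normalised ratio of 1.25 moves it from 1 by 0.2231/1.3863 = 0.161. Requiring a non-significant slope as well brings the joint rate at a true 1.25 to about 5.5% or less for either n.

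**The case against.** A reader might infer that the rule calls changes above 25% negligible far more often than 5% of the time. The documents do not support that as a general statement, for four reasons.

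1. It needs a low CV, and none is given. Above about 30-33% the rate is below 5%. The SAP expects small power. With no true dose effect and n = 25, the rule has 96% power at CV 20% and 51% at CV 30%; where power is about half or less, the error rate is about 7% or less. In reply, the SAP's caution is about missed negligible calls and does not address false ones. Where the rule has useful power, the 240:60 error is inflated.
2. It needs a change close to 1.25 and spread over both steps. The 1.5625 is an arithmetic ceiling, and true ratios of 1.40 or 1.50 seldom pass at CV 20% or above.
3. Cmax and the AUCs have the slope analysis, which looks at the 60-240 mg span. That largely covers these parameters in practice. Its criterion is non-significance, so it sets no bound on the 240:60 ratio, and no slope is planned for the CPL409116/M3 ratios, T1/2, CL/F or Vz/F.
4. The SAP words the criterion for a single interval and claims no error rate over the whole range. Read contrast by contrast, each comparison with 120 mg keeps its 5%. The difficulty is that the conclusion is worded for the dose effect as a whole.

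The percentages also apply only to the one-way by-day model. The model for the dose-normalised parameters adds subject as a fixed effect, and these rates do not carry over to it.

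**Conclusion.** The gap in the rule is real and needs no assumption: 240 mg is not compared with 60 mg, and passing both planned contrasts does not hold the 240:60 ratio within 1.25. The inflation of error is conditional. It exceeds 5% for a true ratio of 1.25 only if the change is spread over both steps and CV is below about 30% (n = 21) or 33% (n = 25). Over assumed CVs of 10-40% with n = 25, the rate runs from about 98% down to 2%. The parameters most exposed are the CPL409116/M3 ratios, T1/2, CL/F and Vz/F. Severity is minor: the analysis is exploratory, is reported with a caution, and feeds no protocol endpoint or decision rule.

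**What to change.** In both places in SAP 4.15, add the 240 mg to 60 mg geometric mean ratio with its 90% interval. State that the dose effect over 60-240 mg is called negligible only if this interval and both intervals against 120 mg lie within 80.00-125.00%. Under the one-way model this holds the rate at a true 240:60 of 1.25 to at most 5% at every CV examined.

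The cost is one more contrast per parameter from data already planned, one sentence in the SAP, and a somewhat lower chance of a correct negligible call. With n = 25 and no dose effect, that chance falls from 96% to 94% at CV 20%, from 78% to 72% at 25%, and from 51% to 44% at 30%.

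### The exploratory PK dose-effect ANOVA fits subject as a fixed effect although each patient takes one dose, so the dose ratios and the 80.00-125.00% decision cannot be estimated from the model as stated

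*SAP*

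**What the plan says.** Section 4.15 of the SAP opens by placing this work outside the protocol: "An exploratory PK analysis, not described in the clinical study protocol, will be performed if data permits". To assess dose proportionality it takes Cmax, AUC(0-inf) and AUC(0-6h) after dose normalisation, together with Vz/F, CL/F and T1/2, all on the log scale. It states that these "will be analyzed using ANOVA with fixed effects for CPL409116 dose, subject and (if applicable) day 1, 8, 57, and 85". Two outputs come from that model. First: "The least square means will be calculated together with 95% CIs". Second: "Estimates of the pairwise geometric means ratios between each dose and the middle dose will be calculated together with 90% confidence intervals". If such a 90% CI lies wholly within 80.00-125.00%, the dose effect is declared negligible.

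Three neighbouring items in section 4.15 matter here:

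- The ANOVA for parent/M3 ratios is fitted "with fixed effects for dose, separately for Days 1, 8, 57, and 85 of the study", with no subject term.
- Intra-subject variability comes from a model "with fixed effects for CPL409116 dose, subject and days 8, 57, and 85 of the study".
- For the log-log regression on dose, "dose-proportionality will be concluded if the slope will not be different from unity".

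SAP section 2.2 randomises each patient to one of four arms, and the protocol synopsis calls the arms parallel. Section 4.2.17 calculates CL/F and Vz/F for Day 85 only. Nothing in the SAP makes subject random, nests it in dose, or names another error term for dose.

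**The concern.** A fixed subject term suits a crossover, where each subject receives several doses and the comparison is made within subject. Here every patient stays on one dose. The subject indicators for one arm add up to that arm's dose indicator, so once subject is in the model dose has nothing left to explain. An explicit decision rule is attached to a contrast that the model cannot estimate.

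The silent failure is the more serious one. Software may still print a dose ratio by averaging subjects within dose. The point estimate is then sound, but the interval ignores variation between patients, which is the error that matters when patients are randomised to doses. An interval that is too narrow fits inside 80.00-125.00% too easily, and dose effects near the margin are called negligible too often.

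**Working it through.** The SAP gives no df, power or sample size for this ANOVA, so there is no stated figure to reproduce.

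**Inputs.** Three active doses; 25 patients per dose (SAP 2.2), or 21 as in the sample-size section (2.3); four PK days (1, 8, 57, 85) or Day 85 only. The CVs are assumptions: between-subject 30, 40, 50% and within-subject 20, 30, 40%, giving nine pairs.

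**Step 1: estimability (follows from the design alone).** Columns for the intercept, dose, subject and day have rank 3n + (days - 1).

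| Patients per dose, days | Records | Rank with dose | Rank without dose | Dose df after subject | Residual df |
|---|---|---|---|---|---|
| 25, four days | 300 | 78 | 78 | 0 | 222 |
| 21, four days | 252 | 66 | 66 | 0 | 186 |
| 25, Day 85 only | 75 | 75 | 75 | 0 | 0 |
| 21, Day 85 only | 63 | 63 | 63 | 0 | 0 |

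The dose contrast and the ordinary dose LS mean are not estimable in any row. An average over each dose's own subjects is estimable. For CL/F and Vz/F the model is saturated, so no interval of any kind exists; that failure is visible.

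**Step 2: what averaging within dose gives (conditional on the CVs and on four complete days).** With v = ln(1 + CV²) and vb, vw the between- and within-subject values:

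- true variance of a log dose difference: 2(vb + vw/4)/n
- variance the fixed-subject model uses: 2(vw/4)/n, with 9n - 3 df

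Example, CVs 30% and 20%, n = 25: vb = ln 1.09 = 0.0862 and vw = ln 1.04 = 0.0392.

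- True SE = √(2 × (0.0862 + 0.0098)/25) = 0.0876.
- Model SE = √(2 × 0.0098/25) = 0.0280.
- The ratio is 3.13, and the nominal 90% CI covers about 40%.

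Over the nine pairs at n = 25, the SE is 1.82 to 4.87 times too small. The 90% CI of a ratio covers 26.5 to 63.4%, and the 95% CI of an LS mean covers 31 to 72%.

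**Step 3: the decision.** Probability that one 90% CI lies within 80.00-125.00%, as a range over the nine pairs:

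| True ratio and model | 25 per dose | 21 per dose |
|---|---|---|
| 1.25, subject fixed, averaged | 18-37% | 18-36% |
| 1.25, subject random, 3(n - 1) df | 0.4-5.0% | 0.1-4.9% |
| 1.00, subject fixed, averaged | 64-96% | 57-93% |
| 1.00, subject random | 1-62% | 0.2-49% |
| 1.00, one-way ANOVA on a single day | 0-43% | 0-29% |

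A simulation of 10,000 trials at CVs 30% and 20%, n = 25, agrees. At a true ratio of 1.25 it gave 0.29 (fixed), 0.05 (random) and 0.05 (one-way); at a ratio of 1 it gave 0.96, 0.62 and 0.42.

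**The case against.** Several points are fair.

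- **Zero df holds only for dose adjusted for subject.** A sequential table with dose entered first shows 2 df. That stands, but the decision uses LS means and ratio intervals, which remain non-estimable.
- **The software is not wholly open.** SAP section 5 assigns everything other than PK parameter calculation to R. *emmeans*, which averages within dose, is named only for efficacy in 4.11.1, and 4.15 names no function.
- **Too-narrow intervals are not the only possible output.** The raw R coefficients compare single reference patients. In one simulated data set the dose coefficient was -0.354 against an arm-mean difference of -0.224, with a 90% CI of -0.70 to -0.01. That interval is wide, so over-declaring negligible effects belongs to the averaging route only. This third route is invalid too.
- **Some parameters may not be multi-day.** Section 4.15 lists AUC(0-inf) and the T1/2 comparison on Day 85, whereas 4.2.17 allows four days. Both need an estimable Kel. With Day 85 data only they fail visibly, so the silent error is clearest for Cmax and AUC(0-6h).
- **The error is largest near the margin.** At a true ratio of 1.5 the averaged interval is called negligible in only 0.3-4.7% of trials at 25 per dose (0.5-5.9% at 21).
- **The SAP already advises caution.** That warning is about small samples and low power. Low power makes a negligible effect harder to declare; the averaging route makes it easier. The caution does not cover estimability.

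**Conclusion.** The concern holds. The non-estimable dose contrast and the saturated Day 85 model follow from the parallel design and need no assumption. The sizes of the SE and decision errors depend on the averaging route, complete four-day data and CVs that the documents do not give.

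This should be corrected, but its reach is limited to exploratory PK inference. The following stand as planned: the protocol PK endpoints, the Day 85 mean and SD evaluations, the parameter-by-dose plots, the dose-normalised values "summarized using descriptive methods by dose treatment arm and study day 1, 8, 57, and 85", the by-day slope estimates, the parent/M3 ratio ANOVA and all efficacy analyses.

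A separate minor point is the slope rule: it takes a non-significant departure from unity as proof of proportionality, although the slope's 90% CI is also to be reported.

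**What to change.** Amend a few words in SAP section 4.15:

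1. For parameters available on several days, use a log-scale mixed model with dose and day fixed and subject random.
2. For CL/F and Vz/F, and for T1/2 or AUC(0-inf) if obtained on Day 85 only, use one-way ANOVA on dose. The section already uses this form for the parent/M3 ratios. Dose then has 2 df, with 72 residual df at 25 per dose (60 at 21).
3. Keep the fixed-subject model only for intra-subject variability, where just the residual is used.
4. For the slope, report the estimate with its 90% CI, and claim proportionality only against a margin that the sponsor prespecifies. No particular margin is proposed here.

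The cost is wider intervals. With no true dose effect, the mixed model meets the criterion in about 1-62% of trials at 25 per dose (0.2-49% at 21), on the assumed CVs. A single-day value carries both variance components, a total CV of √(1.09 × 1.04 - 1) = 37% to √(1.25 × 1.16 - 1) = 67%. One-way ANOVA then meets the criterion in at most about 43% of trials (29% at 21), and in under 5% for six of the nine CV pairs. A negligible dose effect on CL/F or Vz/F could seldom be claimed.

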2.1.2. Secondary objectives

Efficacy:

[figure not shown]
- To determine the effect of CPL409116 at 3 different doses, compared to placebo in subjects with rheumatoid arthritis.
- To assess dose-response and exposure- response relationship for CPL409116.

Safety:

- To evaluate safety and tolerability of CPL409116 administered at doses: 60 mg, 120 mg or 240 mg twice a day for 12 weeks in subjects with RA.

Pharmacokinetics:

- To evaluate pharmacokinetic (PK) parameters for CPL409116 and metabolite M3 in patients with RA.

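### The SAP's slope rule for dose proportionality has no acceptance limits, so a non-significant difference from 1 counts as proof and imprecise data favour the conclusion

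*SAP*

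**What the plan says.** SAP 4.15 lists several ways to assess how exposure scales with dose. One is a linear model of log PK parameter (Cmax, AUC(0-inf), AUC(0-6h)) on log dose, fitted to the parameter "value versus log-transformed CPL409116 dose, separately for day 1, 8, 57, and 85 of the study". For this model, "the mean slope of the log-transformed parameters against log-dose will be estimated and the corresponding 90% CIs will be constructed", and then "dose-proportionality will be concluded if the slope will not be different from unity". No range of acceptable slopes is given.

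The ANOVA bullet earlier in the same list works differently. It compares each dose with the middle dose and calls a dose effect negligible only if the 90% CI of the geometric mean ratio falls completely inside 80.00-125.00%. That bullet ends with a warning that "due to the small planned sample size, power of the above analysis will be small and results should be interpreted with caution". The slope bullet carries no such warning, and the SAP does not say which rule prevails if the two disagree.

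**The concern.** A slope that is not significantly different from 1 may mean that exposure is proportional, or only that the interval is wide. The rule does not separate these cases. When the true slope is not 1, fewer evaluable profiles or more variability widen the interval, make it more likely to cover 1, and so make the conclusion of proportionality more likely. In the ratio rule of the same section, imprecision blocks the claim. In the slope rule, it supports the claim.

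The SAP pre-specifies a conclusion here, not just a description, and the PK report is to be attached to the Clinical Study Report. Dose-response and exposure-response are secondary objectives (Protocol 3.2, SAP 2.1.2), so a false statement of proportionality could mislead their interpretation.

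**Working it through.** **The plan's own figure.** There is none to reproduce: neither document gives a power, error rate or sample size for this analysis.

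**Inputs from the documents**
- Doses of 60, 120 and 240 mg BID (SAP 2.1.2): a 4-fold range in two doublings.
- 25 randomised per active arm (SAP 2.2, "25 are to be randomized to the treatment arm with CPL409116 at a dose of 60 mg BID").
- 21 per arm after the planned 16% dropout (SAP 2.3): 25 × 0.84 = 21.
- One regression per parameter and per day, with a 90% CI. Not different from unity is read as: the 90% CI contains 1.

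**Assumption.** The visible documents give no between-subject CV, so 20% to 80% is shown.

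**Formulas** (n patients per arm)
- σ = √ln(1 + CV²)
- Sxx = n × 2 × (ln 2)² = 0.961n
- SE(slope) = σ/√Sxx, with df = 3n − 2
- P(90% CI contains 1) from the non-central t with non-centrality (slope − 1)/SE

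**Two departures from proportionality**
- 25% excess over the whole 60-240 mg range: slope = 1 + ln(1.25)/ln(4) = 1.161. The dose-normalised ratios to the middle dose are 2^0.161 = 1.118 for 240 mg and 2^−0.161 = 0.894 for 60 mg.
- 25% excess per doubling: slope = 1 + ln(1.25)/ln(2) = 1.322. This is the edge of the SAP's ratio criterion, because each of its comparisons spans one doubling.

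**Worked case, CV 40%, n = 25, slope 1.161.** σ = √ln(1.16) = 0.385. Sxx = 24.0. SE = 0.385/4.90 = 0.0786. t(0.95; 73) = 1.666, so the CI half-width is 0.131. Non-centrality = 0.161/0.0786 = 2.05. The probability of concluding proportionality is 0.350.

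**Probability that the stated rule concludes proportionality**

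| CV | slope 1.161, n = 25 | slope 1.161, n = 21 | slope 1.322, n = 25 | slope 1.322, n = 21 |
|---|---|---|---|---|
| 20% | 0.011 | 0.025 | 0.000 | 0.000 |
| 30% | 0.154 | 0.215 | 0.000 | 0.001 |
| 40% | 0.350 | 0.416 | 0.008 | 0.019 |
| 60% | 0.592 | 0.637 | 0.120 | 0.175 |
| 80% | 0.700 | 0.731 | 0.282 | 0.349 |

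When exposure is truly proportional, the probability is 0.90 whatever the precision. Better data therefore earn no credit when the drug is proportional, and worse data are rewarded when it is not.

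**Agreement with the ratio rule.** At slope 1.161 with n = 25, the slope rule concludes proportionality while the 80.00-125.00% rule is not met in 33%, 49% and 59% of simulated trials at CV 40%, 50% and 60% (20,000 runs, ratio rule run as a one-way ANOVA by day).

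**Rules with limits, n = 25.** Each requires the 90% CI for the slope to lie inside the limits, so the chance of a false conclusion at the limit is at most 5%.
- Limits 0.678-1.322: truly proportional PK passes with probability 98%, 76% and 44% at CV 40%, 60% and 80%.
- Limits 0.839-1.161: truly proportional PK passes with probability 98%, 69% and 30% at CV 20%, 30% and 40%, and almost never at CV 60%, where the half-width of 0.188 exceeds the margin of 0.161.

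**The case against.** The best reply is that the slope is one of several methods. Plots by dose, dose-normalised summaries, the ratio criterion and the slope's own 90% CI will all be reported, so a reader can see imprecision. The analysis is labelled exploratory and outside the protocol, and no primary or secondary endpoint rests on it. All of that is correct and limits the consequence. It does not remove a stated rule that reaches its own conclusion with no limits and no precedence.

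The reply also has force against stronger readings:
- A reader might infer that a 25% over-proportional rise would often be declared proportional. That needs a CV of about 40% or more, which the documents do not supply. At CV 20-30% the figure is 1-22%.
- A reader might take 0.839-1.161 as the SAP's own limits carried to the slope. The SAP compares each dose with the middle dose, a 2-fold step, and never applies 80.00-125.00% to 240 versus 60 mg. By its standard a slope of 1.161 is inside the limits (ratios 1.118 and 0.894), so calling it proportional is not an error on that standard.
- A reader might assume far fewer evaluable profiles per arm, such as 10. AUC(0-inf) does need an acceptable Kel fit (SAP 4.2.17), but no such number has a basis in the documents, and Cmax and AUC(0-6h) do not need Kel.
- A reader might cite the small-power caution as an admission about the slope. It closes the ANOVA bullet and does not refer to the slope rule.
- No passage says that proportionality decides dose selection or exposure margins for a later trial.

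**Conclusion.** The concern holds as a flaw in the decision rule. The slope criterion treats absence of a significant difference as proof and reverses the equivalence logic used beside it; this needs no assumption about variability.

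Its size is conditional. With 21-25 evaluable per arm and an assumed CV of 20/30/40/60/80%, a 25% excess over the full dose range would be called proportional in about 1-3/15-22/35-42/59-64/70-73% of analyses. At the slope matching the SAP's own ratio limits the error is negligible up to CV 30%, 1-2% at 40%, and reaches 12-17.5% at 60% and 28-35% at 80%. These figures assume one log-normal profile per patient per day with equal variance across doses. Given the exploratory status, this is a correction worth making, not a threat to the trial's main conclusions.

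**What to change.** In SAP 4.15, replace the sentence on concluding proportionality with: dose proportionality is concluded only if the 90% CI for the slope lies entirely within pre-specified limits; if the CI lies wholly outside them, exposure is called non-proportional; otherwise the result is inconclusive. The slope, its 90% CI and the implied 240/60 mg dose-normalised ratio are reported in all cases.

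Limits consistent with the existing comparisons to the middle dose are 1 ± ln(1.25)/ln(2) = 0.678-1.322. The sponsor should see what they permit: up to 1.25 × 1.25 = 1.56 for 240 versus 60 mg. If 80-125% is wanted end to end, 0.839-1.161 is the matching range, but it is a new and stricter standard that would rarely be met at CV 40% or more. It should be chosen only if earlier PK data show low variability. Reporting the slope and CI with no binary conclusion is also acceptable. The SAP should also say how the slope and ratio results are read together when they differ.

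The cost is one or two sentences, since the 90% CI is already planned. The downside is that inconclusive results will be more frequent: with 0.678-1.322 and 25 per arm, truly proportional PK would fail to pass in about 2%, 24% and 56% of analyses at CV 40%, 60% and 80%.
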